8.2. PHARMACOKINETICS ASSESSMENT

8.2.1. Blood Samples Collection

8.2.1.1. Collection Schedule

Blood samples (4 mL/time point) for determination of encorafenib, binimetinib and the active metabolite of binimetinib (AR00426032) plasma levels will be collected, during Cycle 1 and Cycle 2, at the following times.

Cycle 1:

- Day 1: T2h (± 10 min) and T6h (± 30 min) post encorafenib/ binimetinib dose.

Dosing and sampling information will consist of the date and time of the first encorafenib and binimetinib dose, the encorafenib and binimetinib dose amount administered, and exact date and time of the PK samples;

Cycle 2:

- Day 1: predose (T0) (just prior to the dose of encorafenib/ binimetinib), T2h (± 10 min) post encorafenib/ binimetinib dose.

Dosing and sampling information will consist of:

- For predose sample:
 - . date and time of the last two previous binimetinib doses (morning/evening) and the current day's binimetinib dose, including the dose amounts taken and exact date and time of the PK samples.
 - . date and time of the last previous encorafenib dose and the current day's encorafenib dose, including the dose amounts taken and exact date and time of the PK samples
- For T2h sample:
 - . date and time of the current day's first encorafenib and binimetinib dose, including the dose amounts administered, and exact date and time of the PK samples.

Blood samples (4 mL per time point) for determination of cetuximab serum levels will be collected, during Cycle 1 and Cycle 2, only at the following times:

Cycle 1:

- Day 1: T2h (± 10 min) and T6h (± 30 min) after the beginning of cetuximab infusion.
- Post dose infusion information should include date, dose, start time, and infusion duration. Any eventual infusion interruptions should also be documented.

Cycle 2:

- Day 1: predose (T0) (just prior the infusion), T2h (± 10 min) after the start of cetuximab infusion.

Dosing and sampling information will consist of:

- Predose sample: collection should occur before the beginning of cetuximab infusion. Information should include date, dose, start time, and infusion duration of the last previous dose of cetuximab and exact date and time of the PK sample.
- For T2h: include the current day's date, dose, start time, and infusion duration of the infusion and exact date and time of the PK sample. Any eventual infusion interruptions should also be documented.

Blood sample collection times are presented in (**Table 16**) and (**Table 17**):

Table 16: Pharmacokinetic sampling times for Encorafenib, Binimetinib and AR0042603

	Cycle 1 Day 1		Cycle 2 Day 1	
	Time after encorafenib/ binimetinib dosing on designated dosing days (h)	2	6	0 (Pre-dose)
PK sample for encorafenib, binimetinib and AR00426032 (4 mL per time point)	x	x	x	x

Abbreviations: h = hours; PK = pharmacokinetic

PK samples will be collected on Cycle 1 Day 1 postdose (encorafenib/binimetinib) at 2 h (± 10 min) and 6 h (± 30 min). PK samples will be collected on Cycle 2 Day 1 predose (just prior to encorafenib/binimetinib dose) and postdose at 2 h (± 10 min). Blood samples for encorafenib/binimetinib PK will be processed to collect plasma.

Table 17: Pharmacokinetic sampling times for Cetuximab

	Cycle 1 Day 1		Cycle 2 Day 1	
Time after the start of cetuximab infusion on designated dosing days (h)	2	6	0 (Pre-infusion)	2
PK sample for cetuximab (4 mL per time point)	x	X	x	X

Abbreviations: h = hours; PK = pharmacokinetic

[figure not shown]
PK samples will be collected on Cycle 1 Day 1 post-infusion (cetuximab) at 2 h (± 10 min) and 6 h (± 30 min). PK samples will be collected on Cycle 2 Day 1 pre-infusion (just prior to infusion of cetuximab) and post-infusion at 2 h (± 10 min). Blood samples for cetuximab PK will be processed to obtain serum. Time points are based on the start of infusion.

The total number of blood samples for analytical determination will be 8 *per* subject, making the total volume of collected blood for pharmacokinetics approximately 32 mL *per* subject.

If a subject receiving any of the treatments defined in this protocol experiences an AE that results in an unscheduled visit or meets the criteria for an SAE, a blood sample for measurement of concentrations of drug-related analytes should be collected, if feasible, if less than 24 hours have elapsed since the last dose of study drug.

Study visits for PK sampling should be scheduled in the morning so that correct predose and postdose PK blood samples can be collected. On the PK visit days, the morning doses of encorafenib and binimetinib, if applicable, **should be taken at the study site, only after collecting the predose PK sample** (for cycle 2). A graphic representation of blood PK sampling for plasma and serum is provided in **Figure 1**.

Figure 1: Graphic representation for pharmacokinetic sampling plan*

**Predose PK samples for cetuximab analysis should be collected just prior the beginning of the cetuximab infusion, regardless of the pre-medication that may be used prior to cetuximab infusion.*

If a vomiting episode occurs within the first 4 hours post-dosing of binimetinib and encorafenib during the day of the last dose prior to collection of PK samples, the exact time (whenever possible) must be noted in the e-CRF. In addition, on Day 1 of cycles 1 and 2 when postdose PK samples are collected, if vomiting occurs, the exact time of the first vomiting episode within the first 4 hours post-dosing on that day must be noted.

8.2.1.2. Technical Handling

Complete instructions for sample processing, handling and shipment will be provided in a separate Laboratory Manual.

Each blood sample will be drawn by direct venipuncture or via an indwelling catheter. Each sample will be 4 mL (according to the Collection Schedule **Table 16**, **Table 17**).

Important points for blood collection:

- Blood sampling from a central venous line is not allowed if this line was used to infuse cetuximab,
- If an indwelling catheter is used for blood collection, approximately 1 mL will be drawn and discarded before sampling,
- Blood samples must be collected from the body side contralateral to the site of the cetuximab infusion,

- Care must be taken to collect blood slowly without causing hemolysis

8.2.2. Samples Handling and shipping

Complete instructions for sample labelling, handling, storage and shipping to the central laboratory will be provided in a separate Laboratory Manual. The samples will be stored in the central laboratory until transfer to the bioanalytical center for analytical determination.

8.2.3. Analytical determination

Analytical determination of encorafenib, binimetinib and the active metabolite of binimetinib (AR00426032) in plasma will be carried out at a designated CRO laboratory using validated LC/MS-MS methods.

Analytical determination of cetuximab in serum will be carried out at a designated CRO laboratory using a validated method.

8.2.4. Sample Storage

Biological samples dedicated to analytical determination will not be discarded before the final clinical study report (CSR) is released and without prior notification to the study manager and authorization of the head of the PK/PD Department of IRPF.

8.3. SAFETY ASSESSMENT

8.3.1. Adverse Events

At screening, any concomitant diseases will be reported as medical history in the e-CRF. At each subsequent visit, the occurrence of AEs since the last visit will be determined by the subject's spontaneous reporting, the Investigator's non-leading questioning and his/her clinical evaluation.

The severity of AEs will be evaluated using the NCI-CTCAE, v.4.03.

All AEs that occur after signature of informed consent through 30 days after the last dose of study drug must be recorded on the AE e-CRF, irrespective of their etiology and relationship to study treatment. Assessment and reporting of AEs is described in detail in **Section 10** and will be

completed at the time points specified in the study flow chart (Main study period and Study extension period flow charts).

8.3.2. Clinical Safety Laboratory Assessments

The local clinical center's laboratory will analyze and report all laboratory safety tests performed at the center to the Investigator who will ensure they are entered in the e-CRF. Clinical laboratory tests will be performed according to the laboratory procedures and the latest updated references. Ranges from the laboratory will be used to identify abnormal values.

Assessments including clinical chemistry, hematology, urinalysis, coagulation, and pregnancy tests do not have to be repeated if performed within 72 hours prior to the first dose on Cycle 1 Day 1.

Additional clinical laboratory tests may be obtained at any time during the study at the Investigator's discretion.

8.3.2.1. Schedule

The laboratory investigations will be carried out as described in **Table 18** for Main study period.

For the Study extension period, the laboratory investigations will be carried out as described in **Table 19**

Table 18: Laboratory schedule_ Main study period

Visit	Screening	C1 D1	C1 D8	C1 D15	C1 D22	Cn D1	Cn D8	Cn D15	Cn D22	End of treatment	Safety Follow-Up ^g (EOS)
Cycle Days	D-28 to D-1	D1	D8	D15	D22	D1	D8 ^h	D15	D22 ^h	Dxx	Dxx
Epochs	SCREENING		TREATMENT								FOLLOW-UP
		Pre-Dose	Post-Dose								
Pregnancy test ^a	X	X ^f				X				X	X
LH, FSH and/or estradiol ^a	X										
Hepatitis B surface antigen, Hepatitis C antibody	X										
HIV (when required)	X										
Hematology ^b	X	X ^f		X	X	X				X	X
Clinical chemistry ^c	X	X ^f		X		X				X	X
Coagulation ^d	X	X ^f				X				X	X
Urinalysis ^e	X	X ^f				X				X	X
Blood Sample for CRP	X										

- a local urine pregnancy test for women of childbearing potential except serum pregnancy test at screening and EOT. For menopausal women only: serum LH,FSH and or estradiol measurement if applicable
- b Hematology - list of analytes: basophils, eosinophils, hematocrit, hemoglobin, lymphocytes, monocytes, neutrophils/absolute neutrophil count (ANC), platelets, red blood cells (RBC), white blood cells (WBC)
- c Clinical Chemistry – list of analytes: alanine aminotransferase (ALT), aspartate aminotransferase (AST), bilirubin [total and direct (*and indirect – only applicable for France*)] ,albumin, alkaline phosphatase, bicarbonate (HCO3)- not mandatory in Japan, blood urea nitrogen (BUN)/urea, calcium, chloride, creatine kinase (CK), creatinine, glucose, lactate dehydrogenase (LDH), magnesium, potassium, sodium, total protein, troponin I or T, uric acid, amylase, lipase.

NOTE: Direct bilirubin (*and indirect – only applicable for France*) will be measured at screening only if total bilirubin values are abnormal; for purposes of determining eligibility to participate in the study.Calculated creatinine clearance (Cockcroft-Gault formula) will be measured at screening
- d Coagulation – list of analytes: prothrombin time (PT) or International Normalized Ratio (INR);activated partial thromboplastin time (aPTT)
- e Urinalysis – list of analytes: blood, glucose, ketones, leukocytes, hydrogen ion concentration (pH), protein
- f Procedure does not have to be repeated if performed within 72 hours prior to Cycle 1 Day 1 (i.e., first day of dosing).

- g To be performed 30-day after end of treatment (EOT) , when clinically appropriate, it is recommended subjects be monitored with physical examinations, dermatological examinations and chest CT scans for cutaneous and non-cutaneous secondary malignancies for up to 6 months after the last encorafenib dose or until initiation of another antineoplastic therapy.
- h From Week 29 (cycle 8), D8 and D22 visits will not be performed (biweekly infusions of cetuximab: no infusions on D8 and D22)

Table 19: Laboratory schedule_Study extension period

Visit	Cn D1	Cn D15	End of treatment	Safety Follow-U^e (EOS)
Cycle Days	D1	D15	Dxx	Dxx
Epochs	TREATMENT			FOLLOW-UP
Pregnancy test ^a	X		X	X
Hematology ^b	X		X	X
Clinical chemistry ^c	X		X	X
Urinalysis ^d	X		X	X

- a local urine pregnancy test for women of childbearing potential except serum pregnancy test at EOT.
- b Hematology - list of analytes: basophils, eosinophils, hematocrit, hemoglobin, lymphocytes, monocytes, neutrophils/absolute neutrophil count (ANC), platelets, red blood cells (RBC), white blood cells (WBC)
- c Clinical Chemistry – list of analytes: alanine aminotransferase (ALT), aspartate aminotransferase (AST), bilirubin (total and direct), albumin, alkaline phosphatase., calcium, chloride, creatinine, glucose, magnesium, potassium, sodium, total protein, Calculated creatinine clearance (Cockcroft-Gault formula)
- d Urinalysis – list of analytes: blood, glucose, ketones, leukocytes, hydrogen ion concentration (pH), protein
- e To be performed 30-day after end of treatment (EOT) , when clinically appropriate., it is recommended that subjects be monitored for physical examinations, dermatological examinations and chest CT scans for cutaneous and non cutaneous secondary malignancies for up to 6 months after the last encorafenib dose or until initiation of another antineoplastic therapy.

8.3.2.2. Parameters

Table 20: Summary of Clinical Laboratory Tests_ Main study period

Hematology	Chemistry	Urinalysis	Coagulation
Basophils Eosinophils Hematocrit Hemoglobin Lymphocytes Monocytes Neutrophils/ANC Platelets RBC WBC	ALT AST Bilirubin [total and direct (and indirect – only applicable for France)] ^a Albumin Alkaline phosphatase Bicarbonate (HCO ₃) BUN/urea Calcium Chloride CK ^b Creatinine Glucose LDH Magnesium Potassium Sodium Total protein Troponin I or T Uric acid Lipase Amylase Serum CK isoenzymes ^b Myoglobin ^b	Blood Glucose Ketones Leukocytes pH Protein Myoglobin ^b	PT or INR aPTT Other At Screening only: 
 • Hepatitis B surface antigen • Hepatitis C antibody • CRP • Calculated creatinine clearance (Cockcroft-Gault formula) • LH, FSH and/or estradiol (if applicable) • HIV (if required) • At Screening and EOT • Serum pregnancy test (if applicable)

Abbreviations: ALT = alanine aminotransferase; ANC = absolute neutrophil count; AST = aspartate aminotransferase; BUN = blood urea nitrogen; CK = creatine kinase; CRP = C-reactive protein; FSH = follicle-stimulating hormone; INR = International Normalized Ratio; LDH = lactate dehydrogenase; LH = luteinizing hormone; pH = hydrogen ion concentration; PT = prothrombin time; aPPT = activated partial thromboplastin time; RBC = red blood cell(s); WBC = white blood cell(s); HIV = Human Immuno deficiency Virus.

^a Direct bilirubin (*and indirect – only applicable for France*) will be measured at screening only if total bilirubin values are abnormal; for the purposes of determining eligibility to participate in the study.

^b For Grade 2 total CK that is also $\geq 3 \times$ ULN or asymptomatic Grade 3 total CK: measure CK, CK isoenzymes and myoglobin in blood or urine weekly for 3 weeks. If total CK remains above the grade that led to the increased monitoring, continue to assess CK, CK isoenzymes and myoglobin, along with regularly scheduled clinical chemistry assessments, until normalization or improvement to Grade 1. When CK is elevated, ensure the subject is adequately hydrated.

Table 21: Summary of Clinical Laboratory Tests_Study extension period

Hematology	Chemistry	Urinalysis	Other
Basophils Eosinophils Hematocrit Hemoglobin Lymphocytes Monocytes Neutrophils/ANC Platelets RBC WBC	ALT AST Bilirubin [total and direct (and indirect – only applicable for France)] Albumin Alkaline phosphatase Calcium Chloride Creatinine Glucose Magnesium Potassium Sodium Total protein	Blood Glucose Ketones Leukocytes pH Protein	At EOT Serum pregnancy test (if applicable)

Abbreviations: ALT = alanine aminotransferase; ANC = absolute neutrophil count; AST = pH = hydrogen ion concentration; RBC = red blood cell(s); WBC = white blood cell(s)

Hematology, Coagulation and Clinical Chemistry:

Blood samples for the hematology, coagulation and chemistry laboratory tests listed in Table Summary of Clinical Laboratory Tests (**Table 20**) will be collected at the time points specified in Table Laboratory Schedule (**Table 18**) for Main study period.

For the Study extension period, blood samples for the hematology and chemistry laboratory tests listed in Table Summary of Clinical Laboratory Tests (**Table 21**) will be collected at the time points specified in Table Laboratory Schedule (**Table 19**).

Blood sample collections occurring on dosing days must be performed prior to study drug administration. Laboratory test results required to make decisions regarding potential dose modifications (as specified in **Section 6.5.4**) should be reviewed prior to study treatment administration.

Additional tests may be done at the Investigator's discretion, in the subjects' best interest.

Urinalysis

Urine samples for the laboratory tests listed in Summary of Clinical Laboratory Tests (**Table 20**) for Main study period will be collected at the time points specified in Table Laboratory Schedule (**Table 18**).

Urine samples for the laboratory tests for the Study extension period listed in Summary of Clinical Laboratory Tests (**Table 21**) will be collected at the time points specified in Table Laboratory Schedule (**Table 19**).

All urine collections occurring on dosing days must be performed prior to study treatment administration.

Pregnancy and Assessment of Fertility

For Main study and Study extension periods, all females of childbearing potential are required to undergo a local serum pregnancy assessment at Screening and end of treatment (EOT) and local urine pregnancy assessments at time points specified in Table Laboratory Schedule (**Table 18 and Table 19**)

Any positive pregnancy tests will result in immediate cessation of study treatment administration. Female subjects of non-childbearing potential (as defined in **Section 5.3**) do not require pregnancy tests.

8.3.3. Physical Examination

A physical examination will be carried out for each body system at the screening visit and on Day 1 of every cycle (for Main study and Study extension periods).

At Screening, the physical examination should include general appearance, skin, neck (including thyroid), eyes, ears, nose, throat, lungs, heart, abdomen, back, lymph nodes, extremities, vascular and neurological. If indicated based on medical history and/or symptoms, rectal, external genitalia, breast and pelvic examinations will be performed; body weight will be measured as part of the physical examination. Height will only be measured at Screening.

For subsequent visits, the physical examinations should be targeted as clinically indicated.

The physical examination will be globally evaluated prior to study drug administration as “normal/abnormal”. Further target inspection will be undertaken for any abnormal finding and will be recorded as AEs.

8.3.4. Vital Signs

8.3.4.1. *Schedule*

Vital signs include Heart Rate (HR), systolic and diastolic blood pressure (SBP, DBP), respiration rate, and temperature. They will be assessed at the time points indicated in the study flow chart (please refer to the flow-chart corresponding to the current period: Main study or Study extension).

8.3.4.2. *Technical Procedure and Parameters*

SBP and DBP, expressed in mmHg, and HR expressed in beat per minute (bpm) will be measured per institutional standards.

Limits for abnormal values for SBP and DBP should be graded according to NCI-CTCAE, v.4.03 as described in tables below (Table 22 and Table 23).

Table 22: Modified NCI CTCAE, Version 4.03 Grading for Hypertension

Grade	Description
Grade 1	Prehypertension (systolic BP 120-139 mm Hg or diastolic BP 80-89 mm Hg)
Grade 2	Stage 1 hypertension (systolicBP 140 - 159 mm Hg or diastolic BP 90 - 99 mm Hg); medical intervention indicated; recurrent or persistent (≥ 24 hrs); symptomatic increase by >20 mm Hg (diastolic) or to $>140/90$ mm Hg if previously WNL; monotherapy indicated
Grade 3	Stage 2 hypertension (systolic BP ≥ 160 mm Hg or diastolic BP ≥ 100 mm Hg); Medical intervention indicated; more than one drug or more intensive therapy than previously used indicated
Grade 4	Life-threatening consequences (e.g., malignant hypertension, Transient or permanent neurologic deficit, hypertensive crisis); urgent intervention indicated

Definition: A disorder characterized by a pathological increase in blood pressure; a repeatedly elevation in the blood pressure exceeding 140 over 90 mm Hg.

Table 23: Modified NCI CTCAE, Version 4.03 Grading for Hypotension

Grade	Description
Grade 1	Asymptomatic, intervention not indicated
Grade 2	Non-urgent medical intervention indicated
Grade 3	Medical intervention or hospitalization indicated
Grade 4	Life-threatening and urgent intervention indicated

Definition: A disorder characterized by a blood pressure that is below the normal expected for an individual in a given environment.

An institutional thermometer will be used to measure body temperature.

All vital sign measurements occurring on dosing days must be performed prior to study treatment administration.

Any treatment-emergent abnormal findings will be recorded as AEs.

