10. ADVERSE EVENTS: DEFINITION, NOTIFICATION AND REPORTING

10.1. ADVERSE EVENTS

10.1.1. Definition

An AE is any untoward medical occurrence, including the exacerbation of a pre-existing condition, in a patient or clinical investigation subject administered a pharmaceutical product and which does not necessarily have a causal relationship with this treatment.

An AE can therefore be any unfavorable and unintended sign (including an abnormal laboratory finding), symptom, or disease temporally associated with the use of a medicinal (investigational) product, whether or not related to the medicinal (investigational) product (ICH-Guideline for GCP).

Any new or worsening adverse event that is assessed by the investigator as related to the disease progression must be reported as an AE.

The relationship to disease progression must be captured as specified in e-CRF.

If the AE meets the seriousness definition and thus becomes SAE, it should be notified to the Sponsor Pharmacovigilance Department by the investigator as soon as he/she is informed of the event and no later than 24 hours after knowledge.

Note: Disease progression documented solely by medical imaging techniques with no new or worsening symptoms will not require to be reported as an AE nor notified as SAE to the Sponsor Pharmacovigilance Department but documented as progression of disease in the tumor assessments (RECIST) e-CRF forms.

All laboratory tests, vital signs, ECGs collected after study treatment initiation for which abnormal results meet the criteria for AE are collected after study treatment initiation should be repeated until the values return to normal or to a stable status and recorded into the e-CRF.

The frequency with which such checks should be made will be defined by the investigator according to the degree of abnormality.

For any of the following reasons, an abnormal result should be considered as clinically significant and reported as an AE. :

- A symptomatic value.
- A value or a change that requires active management (e.g., study treatment dose modification, discontinuation of study treatment, more frequent follow-up assessments, corrective treatment ...).
- Any value judged by the investigator as clinically significant.

Laboratory abnormalities that meet the criteria for AEs should be followed until they have returned to normal or baseline, or per Investigator discretion.

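### Protocol 8.3.4.2 and 10.1.1 set different tests for when an abnormal vital sign becomes an adverse event, so Grade 1-2 hypertension counts may depend on site practice (minor)

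*Protocol*

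**What the plan says.** **Protocol 8.3.4.2 (vital signs).** The section states: "Limits for abnormal values for SBP and DBP should be graded according to NCI-CTCAE, v.4.03 as described in tables below". Table 22 then places systolic 120-139 or diastolic 80-89 mmHg in Grade 1. The definition line under the same table describes the event differently, as "a repeatedly elevation in the blood pressure exceeding 140 over 90 mm Hg". Table 23, for hypotension, gives no numeric limits. The section closes with "Any treatment-emergent abnormal findings will be recorded as AEs", without any test of clinical significance.

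**Protocol 10.1.1 (definition of an AE).** Vital signs are named: "All laboratory tests, vital signs, ECGs collected after study treatment initiation for which abnormal results meet the criteria for AE" are to be repeated until normal or stable and recorded. It continues: "For any of the following reasons, an abnormal result should be considered as clinically significant and reported as an AE". Three reasons follow: the value is symptomatic, it or its change requires active management, or the investigator judges it clinically significant.

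**Link between them.** Section 8.3.1 says that AE assessment and reporting are detailed in Section 10. Sections 8.3.4.2 and 10.1.1 do not refer to each other.

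**Outputs.** Type and severity of AEs is a secondary endpoint (Protocol 2.5). Protocol 13.9.2 and SAP 15.2 count subjects with reported treatment-emergent AEs by preferred term and maximum grade. SAP 15.4 separately tabulates blood-pressure grade shifts and clinically notable values from the measurements themselves.

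**The concern.** The two sections give investigators different instructions for the same reading. Read literally, 8.3.4.2 makes an AE of any on-treatment value that moves into Table 22. Section 10.1.1 asks first whether the value matters clinically. With about 70 centers in three regions, both practices could occur within one study.

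The AE tables count what sites report, so they inherit whichever rule each site applied. Hypertension is a term that readers will look for: Protocol Table 4 gives it in 6% (Grade 1-2) and 7% (Grade 3) of subjects on single-agent binimetinib, and Table 5 gives 11.3% and 8.2% for the two encorafenib-binimetinib combinations. If low-grade events here were recorded under a mixture of rules, the overall hypertension rate would be hard to interpret.

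**Working it through.** The documents state no expected hypertension rate, so there is no planned figure to reproduce. The check is to apply both sections to the same readings.

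**Inputs**
- Abnormality limits: Table 22, Grade 1 at 120-139 or 80-89 mmHg, Grade 2 at 140-159 or 90-99, Grade 3 at 160 or more or 100 or more.
- Rule A: last sentence of 8.3.4.2.
- Rule B: the three reasons in 10.1.1.

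**Illustrative readings (baseline 115/75 mmHg, Grade 0)**

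| On-treatment reading | Table 22 numeric grade | Rule A | Rule B |
|---|---|---|---|
| 122/78, no symptoms, no action | 1 | AE | Not an AE unless judged clinically significant |
| 144/86 once, no symptoms, no action | 2 | AE | Not an AE unless judged clinically significant |
| 162/98, treated | 3 | AE | AE (active management) |

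The first reading adds 1 to the hypertension count under Rule A and, absent a judgement of clinical significance, 0 under Rule B. The third adds 1 under both.

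**Where the rules part.** They diverge for readings that are asymptomatic, unmanaged and not judged significant. These are mostly Grade 1, with some isolated Grade 2. Table 22 describes Grade 3 and 4 as calling for intervention, so such values would normally be AEs under either rule.

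**Does Table 22 settle it?** No. Its definition line speaks of repeated elevation above 140/90, under which neither of the first two readings is a hypertension event. Its Grade 1 row starts at 120/80, under which both are graded. A site could defend either.

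**Does 8.3.1 settle it?** Partly. It directs AE reporting to Section 10, which favors Rule B. It does not say that Section 10 overrides a specific instruction in 8.3.4.2.

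**Which tables move?** Treatment-emergent AE tables by preferred term and maximum grade can change at Grades 1-2. The Grade 3 or higher columns of SAP 15.2 should change little. The SAP 15.4 shift table uses the same 120/80 cut-offs but is built from recorded pressures. The notable-value table uses, for example, systolic 160 or more with a rise of at least 20 mmHg (SAP Appendix 4). Neither depends on whether the site entered an AE.

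**The case against.** The strongest reply is that the protocol already has a governing section. Section 8.3.1 sends AE assessment and reporting to Section 10, and 10.1.1 expressly covers vital signs. A trained site would apply 10.1.1 and treat 8.3.4.2 as loose wording. Table 22's own definition also excludes a single reading of 122/78. This is a fair reading, and it makes universal literal use of 8.3.4.2 unlikely. It does not remove the instruction in 8.3.4.2, which carries no condition and sits beside the measurement it governs.

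Three stronger readings are tempting, and the documents do not support them.

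- **That 10.1.1 restricts AEs to clinically significant values.** It lists reasons that make a result reportable and never says only. One reason is investigator judgement, and the general definition covers any unfavorable sign. The restriction is implied, not stated.
- **That hypertension AEs would be inflated by a known, large amount.** A simulation with no drug effect can put 36-57% of subjects in a higher Table 22 grade than at baseline at least once over 8 visits, and 50-75% over 28. It needs assumed inputs (mean 120-128/73-77 mmHg, between-subject SD 10-14/6-8, within-subject SD 5-9/4-6), none of which the documents supply. It counts every single upward crossing under Rule A, not the difference between the rules, and the 28-visit case assumes full weekly attendance. At most it is an upper bound conditional on those inputs.
- **That hypotension and physical findings are equally affected.** Table 23 has no cut-off to cross. The sentence in 8.3.3, "Further target inspection will be undertaken for any abnormal finding and will be recorded as AEs", is grammatically unclear, and the vital-signs sentence of 10.1.1 does not mention physical examination.

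**Conclusion.** The inconsistency is real and minor. Section 8.3.4.2 records any treatment-emergent abnormal vital sign as an AE. Section 10.1.1, to which 8.3.1 refers, applies a test of symptoms, management or judgement, and no clause states precedence. Asymptomatic, unmanaged low-grade readings may therefore be recorded differently between sites, which would make Grade 1-2 hypertension counts inconsistent.

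The conclusion rests on the wording alone and assumes only that some sites could follow each section. Its size cannot be derived from the documents. Nor do they show that comparison with earlier binimetinib data is invalid: the AE-recording rules of those studies are not given, and Table 5 concerns melanoma. The confirmed response rate is unaffected.

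**What to change.** Replace the last sentence of 8.3.4.2 with: *Treatment-emergent abnormal findings that meet the criteria of Section 10.1.1 will be recorded as AEs; Tables 22 and 23 are used to grade them.* Issue a short memo to sites. Aligning 8.3.3 in the same way is optional tidying.

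The cost is one sentence of protocol text and the memo. No new data are needed, and no reading is lost, because all measured pressures still feed SAP 15.4. For data already collected, the study report should present low-grade hypertension AE rates beside the SAP 15.4 shift and notable-value tables and note that the recording rule may have varied between sites.
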